Continuation of Low-Dose Aspirin Therapy with Either PR or PO Administration in Patients with Peptic Ulcer Bleeding

IRB Protocol
[name]
February 4, 2010

A. Study Design and Purpose

Aspirin has been well established to reduce the risk of subsequent vascular events in patients with previous ischemic events by 22%[1]. However aspirin also increases the risk of Peptic ulcer bleeding by 2 to 3 fold [2]. Enteric coded aspirin has not been shown to decrease this risk of bleeding[3]. Switching to other antiplatelet agents, such as clopidogrel, has not decreased rates of peptic ulcer bleeding[4].

Based on the risk of aspirin associated with peptic ulcer bleeding, the standard protocol, when a patient presents with a bleed, is to stop aspirin until the ulcer has fully healed [5]. A recent study suggests that there may be a mortality benefit of continuing aspirin during a peptic ulcer bleed, if the bleeding was controlled, and that might outweigh the increased risk of recurrent bleeding. The study suggested that although the risk of rebleeding roughly doubled, there was 11.6 absolute difference in mortality reduction. Based on this study, if the risk of rebleeding could be reduced, there may be further mortality and morbidity benefit.[5]

It has been postulated that aspirin induces the effect of increased peptic ulcer bleeding in 2 ways: it causes irritation and injury to the gastric mucosa and a systemic effect [3]. This effect is mediated through the inhibition of cyclooxygenase enzymes which decrease production of prostaglandin PG E2 which protects the upper gastrointestinal tract by increasing mucous and bicarbonate secretion, surface epithelial cell hydrophobicity and mucosal blood flow[10]. It is believed that there is a local effect on the mucosa by aspirin. Although the mechanism has not been fully elucidated, it is hypothesized to be secondary to increased local prostaglandin suppression [11]. If a patient were to take rectal aspirin, this may decrease the local effect, thereby decreasing the rebleeding rate. There have been studies that showed that rectal administration of aspirin can achieve the same blood levels as po administration [6]. In this study, we hypothesize that if patients with peptic ulcer bleeding suspected to be caused by aspirin, are switched to rectal aspirin instead of continuing with oral aspirin, their rate of rebleeding will decrease.

B. Study Design and Statistical Analysis

Patients will be randomly assigned to either rectal or po administration of aspirin in a 1:1 fashion in this multi-center, double blind, randomized control trial. The patients will receive both a po and rectal pill daily, one will be a placebo and the other pill will be active depending on the group to which they are assigned. This allows for both the patient and the physician to be blinded. The random allocation sequence will be generated by the Department of Medical statistics with the blocked randomization method.

The primary outcome will be recurrent bleeding within the 30 days after endoscopic treatment. This will be defined as having clinical evidence of rebleeding, which includes: hematemesis, melena after normal stool, hemoglobin drop of 2 or more g/dl in a 24 hour period, requiring 2 or more units of blood in, or unstable vital signs (hypotension systolic bp less than 90 or tachycardia greater than 110) and another endoscopy confirming bleeding (arterial spurter, nonbleeding visible vessel, adherent clot, or fresh blood in the stomach).

Secondary outcomes will include all cause mortality, death attributed to cardiovascular, cerebrovascular or gastrointestinal complication, ischemic events (defined by the American College of cardiology guidelines for cardiac events and the WHO cerebrovascular criteria) [7,8], lower gastrointestinal bleeding, and aspirin blood levels in the two groups.

In order to achieve 80% power with a P value of 0.05, a sample size of 1422 people in each group was calculated using the Chi-square test assuming minimal clinically significant effect size of a 7% versus 10% risk of rebleeding in the rectal versus po aspirin groups. Data will be analyzed using the Chi-squared test when calculating the primary outcome and a t-test to compare group differences.

C. Study Procedure

Consecutive patients who present with signs suggestive of upper gi bleeding (melena, hematemesis), will be screened and if eligible (as described in the study subject section -- having signs of peptic ulcer bleeding that are successfully treated with endoscopic procedure and are on aspirin for secondary prevention), will be randomized to either 300mg aspirin administered rectally or 81 mg po aspirin [9]. Then they will have an endoscopic exam that will identify that the patient has an upper gastrointestinal bleed, treat the bleed and prove that it is controlled. This must be done within 24 hours of onset of upper gastrointestinal bleeding. They will also be treated with standard therapy for ulcer bleeding, meaning intravenous esomeprazole of 80 mg followed by an infusion of esomeprazole 8mg/h for 72 hours and then transition to 40 mg/d orally. They then will be followed for signs of rebleeding, as described above. If clinical signs were met, the patient would undergo endoscopy to evaluate if the criteria for a rebleed are met. They will also be followed for signs of lower gastrointestinal bleeding, which include the same clinical criteria as for upper bleeding described above, plus bright red blood per rectum. Blood levels of aspirin will be measured at day 1, 15, 30. The care of the patient will be led by the medical teams at the hospital where the patient was admitted while the patient is in the hospital, and that team will determine when the patient is ready for discharge.

The patient will be required to make a clinic visit with a study physician at 15 and 30 days if not still in the hospital, when blood will be drawn. Patients will be advised on what may be signs of rebleeding and educated that they should emergently to go to the hospital if they have those signs.

D. Study Drugs

Aspirin is a white tablet that has many different strengths. In this study, an 81 mg tablet will be taken by mouth and a 300mg tablet that will be administered rectally. There have been many studies on the efficacy and toxicity of aspirin, as discussed in the review section. The toxicity being tested in this study will be gastric mucosa damage leading to impaired healing and increased rebleeding rates.

Inactive ingredients in the tablets will include carnauba wax, corn starch, hypromellose, powdered cellulose, and triacetin. The appropriate number of tablets will be dispensed at time of discharge from their hospital visit. A pill count will also be performed at the 30 day visit to ensure compliance with study medications.

E. Medical Device

Not applicable.

F. Study Questionnaires

Not applicable

G. Study Subjects

Inclusion criteria: Patients must be 18 or older and must have peptic ulcer on endoscopy showing active bleeding, visible blood vessels, or adherent clots that were successfully treated by endoscopic therapy and continue to require low dose aspirin for prophylaxis or treatment of cardiovascular disease. The indications for low dose aspirin include prophylaxis of established cardiovascular or cerebrovascular disease that requires regular anti-platelet therapy.

Exclusion criteria: Aspirin use for primary prevention. Any patient whose bleeding was not controlled with hemostasis during endoscopy, with ulcer perforation, known sensitivity to ppi, previous gastrectomy, or vagotomy, patients on concomitant anticoagulant, corticosteroids, NSAIDs, patients who are pregnant, or have a GFR less than 30 at the time of admission.

H. Recruitment of Subjects

Patients will be recruited at the time of admission for suspected upper gastrointestinal bleeding in the emergency department at CPMC, Weill Cornell, Mount Sinai, and NYU medical center.

I. Confidentiality of Study Data

All study data will be stored in a confidential manner. All study materials will be coded with a unique subject identifier, as assigned in the study. This will not include any personal identifiers.

J. Potential Conflict of Interest

There are no conflicts of interest.

K. Location of Study

The study will be conducted in the hospital setting of the following hospitals: CPMC, Weill Cornell, Mount Sinai, and NYU medical center and in the clinic of the study physicians office at CPMC.

L. Potential Risks

Potential risks include: the increased risk of bleeding when taking aspirin while having a bleeding ulcer. This may lead to death or increased hospital stay. There is also the mental discomfort, physical discomfort from blood drawing or taking a medication rectally.

M. Potential benefits

The main effect would be that rectal aspirin would decrease the risk of rebleeding, while preserving the mortality benefit of aspirin in this high risk patient population.

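### Section C contradicts itself and Section G on whether randomisation comes before or after the index endoscopy that decides eligibility

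*Protocol*

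**What the plan says.** Section C (Study Procedure) screens consecutive patients who present with melena or hematemesis. Those who are eligible are randomised to the rectal or the oral arm, and a parenthesis in the same sentence lists successful endoscopic treatment as part of eligibility. The next sentence, whose last requirement is proof of control, begins: "Then they will have an endoscopic exam that will identify that the patient has an upper gastrointestinal bleed, treat the bleed and prove". This is the index endoscopy. The repeat endoscopy for suspected rebleeding is described separately, later in the section.

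Section G (Study Subjects) requires that patients "must have peptic ulcer on endoscopy showing active bleeding, visible blood vessels, or adherent clots that were successfully treated by endoscopic therapy". It excludes "Any patient whose bleeding was not controlled with hemostasis during endoscopy".

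Section H (Recruitment of Subjects) places recruitment in the emergency department, at admission for a suspected bleed. It does not say that randomisation takes place there.

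Section B (Study Design and Statistical Analysis) starts the outcome clock at treatment: "The primary outcome will be recurrent bleeding within the 30 days after endoscopic treatment". On size it says that "a sample size of 1422 people in each group was calculated using the Chi-square test". The rates behind that figure are 7% with rectal aspirin and 10% with oral aspirin.

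**The concern.** Whether there is an ulcer with the required signs, and whether its treatment succeeded, is unknown until the endoscopy is over. A randomisation step that depends on those facts cannot come before the procedure that establishes them, yet Section C puts it there.

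Four hospitals would work from this text. One that follows the sequence randomises on clinical suspicion, and one that follows the eligibility clause randomises after hemostasis. These are different trial populations.

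Under the first reading, some randomised patients would fail Section G. Those given no endoscopic treatment would also have no day from which to count 30 days. If such patients are dropped, the analysed number is below 1422 per group. If they are kept, they dilute the contrast between the arms. The order of allocation and endoscopy is trial conduct and belongs in the protocol, so a statistical analysis plan could not repair it.

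**Working it through.** **Order of steps, side by side**

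- Section C, eligibility clause: endoscopic treatment has succeeded, then randomise.
- Section C, next sentence: randomise, then endoscopy identifies, treats and proves control.
- Section G: ulcer signs and successful treatment are entry conditions, and uncontrolled bleeding is an exclusion.
- Section B: the 30 days run from endoscopic treatment.

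The first, third and fourth presuppose a treated bleed at entry. The second reverses the order.

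**The plan's own sample size**

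Inputs from Section B: 7% versus 10%, 80% power, significance level 0.05, and 1:1 allocation. The protocol does not state whether the test is one- or two-sided; two-sided is taken because it reproduces the figure.

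Without continuity correction, with mean rate 0.085:

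n = [1.960·√(2·0.085·0.915) + 0.842·√(0.07·0.93 + 0.10·0.90)]² / 0.03², which gives 1356.

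With continuity correction:

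n′ = (n/4)·[1 + √(1 + 4/(n·0.03))]² = (1356/4)·[1 + √1.0983]², which gives 1422.

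The stated figure is reproduced exactly and is not in dispute. It contains no allowance for patients found ineligible after randomisation.

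**Effect if the written order is followed**

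Let f be the share of randomised patients found ineligible at endoscopy. The protocol gives no value, so f is an assumption. Power is two-sided and uncorrected:

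Power = Φ{[|p₁ − p₂|·√n − 1.960·√(2·p̄·(1 − p̄))] / √(p₁(1 − p₁) + p₂(1 − p₂))}

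At n = 1422 with 7% versus 10%: (0.03·37.709 − 0.7730)/0.3938 = 0.910, so power is 81.9%. The continuity-corrected calculation that produced 1422 targets 80%.

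| f (assumed) | Left per group if dropped | Power, dropped | Power, kept as non-events | Power, kept at 8.5% in both arms |
|---|---|---|---|---|
| 0% | 1422 | 81.9% | 81.9% | 81.9% |
| 10% | 1280 | 77.7% | 77.3% | 73.3% |
| 20% | 1138 | 72.8% | 72.0% | 63.1% |
| 30% | 995 | 67.0% | 65.8% | 51.9% |
| 50% | 711 | 52.7% | 50.9% | 29.9% |

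Example, dropped, f = 30%: n = 1422·0.7 = 995, and (0.03·31.544 − 0.7730)/0.3938 = 0.440, so power is 67.0%.

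Example, kept at 8.5%, f = 30%: the rates become 0.7·7% + 0.3·8.5% = 7.45% and 0.7·10% + 0.3·8.5% = 9.55%. The difference shrinks from 3 to 2.1 percentage points, and power is 51.9%. The 8.5% is the mean of the two design rates and is also an assumption.

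To keep the written order, drop ineligible patients and still analyse 1422 per group, the trial would have to randomise 1422/(1 − f) per group: 1580, 1778, 2032 or 2844 for f = 10%, 20%, 30% or 50%.

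**The case against.** The strongest reply is that endoscopy first was plainly intended. The randomising sentence is conditional on eligibility, Section G describes treatment as already done, Section B counts from treatment, and the rationale in Section A speaks of bleeding that was controlled. Only one sequencing word points the other way. This stands as evidence of intent and limits what may be claimed, but it does not remove the contradiction. That word orders the steps in the section that sites follow, and nothing elsewhere corrects it.

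Several stronger readings are tempting and are not supported:

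- A reader might infer that every patient with another diagnosis or failed hemostasis enters the trial as written. The eligibility clause bars such patients, so this follows only if a site obeys the sequence over the clause.
- A reader might infer that many randomised patients would be ineligible. Melena or hematemesis is a broader group than treated high-risk ulcers, but the protocol gives no share. At 5% ineligible and dropped, power is still about 80% uncorrected.
- Section H might be taken as confirming early randomisation. It speaks of recruitment, which is compatible with screening and consent at admission.
- It might be said that all ineligible patients lack a time zero. A patient whose endoscopic treatment failed has a treatment time. The gap concerns only those given no endoscopic treatment.
- It might be inferred that aspirin would be given before bleeding is controlled. Allocation is not dosing, and Section C gives no time for the first study dose.

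How ineligible patients would be treated in the analysis may be set out in a statistical analysis plan that is not at hand, so its absence here is not part of this point.

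**Conclusion.** The point holds as an internal contradiction. Section C cannot be carried out as written, because it randomises on facts that its next step is meant to establish, and Section G conflicts with that order too. This rests on the text alone and needs no assumption.

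The size of the consequence is conditional. It arises only where sites follow the written order, and it depends on an ineligible share that the protocol does not give. For assumed shares of 10% to 50%, power falls from 81.9% to between about 78% and 53% if these patients are dropped. Keeping them with an equal event rate in both arms gives lower power in every case calculated. If sites randomise only after endoscopy has confirmed eligibility, this loss does not arise and 1422 per group stands. The contradiction should be removed before enrolment, since the population randomised cannot be changed afterwards.

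**What to change.** Amend Section C and reconcile it with Section G:

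- Screening and consent may take place at admission, so Section H can stand.
- The allocation is opened only after endoscopy has confirmed that the Section G criteria are met.
- In Section B, state that 1422 per group counts patients randomised at that point.

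The existing 30-day clock from endoscopic treatment can then stay, since every patient properly randomised will have a treatment time. Moving day 0 to randomisation would be optional.

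The cost is a short amendment and a slightly later allocation, with no extra procedure and no extra patients. If the sponsor prefers to randomise before endoscopy, the protocol should say so, define how patients found ineligible afterwards are handled, and enlarge the sample size using a justified ineligible share.

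### The lower gastrointestinal bleeding outcome reuses the upper-bleeding signs and does not exclude a confirmed upper source, so read literally it can mask or reverse a rectal harm

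*Protocol*

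**What the plan says.** Section B lists among the secondary outcomes "lower gastrointestinal bleeding, and aspirin blood levels in the two groups". The only description of that bleeding outcome is in Section C: patients are followed for "signs of lower gastrointestinal bleeding, which include the same clinical criteria as for upper bleeding described above, plus bright red blood per rectum".

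The criteria referred to are those of the primary outcome in Section B: "clinical evidence of rebleeding, which includes: hematemesis, melena after normal stool, hemoglobin drop of 2 or more g/dl in a 24 hour period", together with a transfusion criterion and unstable vital signs. For the primary outcome these signs are not enough. Section B also requires "another endoscopy confirming bleeding (arterial spurter, nonbleeding visible vessel, adherent clot, or fresh blood in the stomach", and Section C gives the order: "If clinical signs were met, the patient would undergo endoscopy to evaluate if the criteria for a rebleed are met".

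For lower bleeding the protocol states no counterpart to that confirmation. It does not attribute the source, does not exclude an episode whose upper source was confirmed, and does not say whether one sign is enough or whether rectal blood must accompany another sign.

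**The concern.** The trial moves aspirin from the mouth to the rectum because of a suspected local effect on the upper mucosa (Section A). Lower gastrointestinal bleeding is the only listed outcome specific to the new site of administration, so a local rectal harm would have to show there.

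As described, the outcome borrows its signs from the primary outcome. Hematemesis points to an upper source. Melena, a hemoglobin drop, transfusion and unstable vital signs do not locate the bleed. If any one sign suffices, an upper rebleed is also a lower bleed. Any upper benefit of the rectal route then carries over into the safety outcome and offsets a true excess of rectal bleeding. The bias runs in the direction of the trial's own hypothesis.

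**Working it through.** **Inputs from Section B.** Upper rebleeding: "7% versus 10% risk of rebleeding in the rectal versus po aspirin groups". Size: 1422 per group, 1:1. Error rates: "In order to achieve 80% power with a P value of 0.05".

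**Inputs assumed.** The protocol gives no lower-bleeding rates, so they are varied below. Upper and lower bleeding are taken as independent, and only endoscopically confirmed upper rebleeds are carried over.

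**1. The protocol's own figure.** For 7% against 10%, two-sided 0.05 and 80% power, the two-proportion formula gives 1356 per group without a continuity correction and 1422 with it. The stated size reproduces exactly with the correction.

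**2. Upper rebleeds entering the lower count.** Rectal: 1422 × 0.07 = 99.5, about 100. Oral: 1422 × 0.10 = 142.2, about 142.

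**3. Rate as counted when any one sign suffices.** With U the upper rate and L the true lower rate, the counted rate is 1 − (1 − U)(1 − L).

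- Equal rates of 1%: rectal 1 − 0.93 × 0.99 = 0.0793; oral 1 − 0.90 × 0.99 = 0.1090.
- 2.5% rectal, 1.0% oral: rectal 1 − 0.93 × 0.975 = 0.0933; oral 0.1090.

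With a and b the counted rectal and oral rates, z = (a − b) / √[a(1 − a)/1422 + b(1 − b)/1422]. Differences are rectal minus oral, in percentage points.

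| True rectal % | True oral % | True difference | Counted rectal % | Counted oral % | Counted difference | z |
|---|---|---|---|---|---|---|
| 1.0 | 1.0 | 0 | 7.93 | 10.90 | −2.97 | −2.72 |
| 1.0 | 0.5 | +0.5 | 7.93 | 10.45 | −2.52 | −2.33 |
| 2.0 | 1.0 | +1.0 | 8.86 | 10.90 | −2.04 | −1.82 |
| 2.5 | 1.0 | +1.5 | 9.33 | 10.90 | −1.58 | −1.39 |
| 3.0 | 1.0 | +2.0 | 9.79 | 10.90 | −1.11 | −0.97 |
| 4.0 | 2.0 | +2.0 | 10.72 | 11.80 | −1.08 | −0.91 |
| 6.0 | 1.0 | +5.0 | 12.58 | 10.90 | +1.68 | +1.39 |

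**4. Where the sign turns.** The counted rates are equal when the true rectal rate is 1 − 0.90 × (1 − L oral)/0.93.

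- Oral 0.5%: 1 − 0.8955/0.93 = 3.7%.
- Oral 1%: 1 − 0.8910/0.93 = 4.2%.
- Oral 2%: 1 − 0.8820/0.93 = 5.2%.

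In each case the true rectal excess must pass about 3.2 points before the outcome points towards harm. Above that the direction is right but the size is diluted, as in the last row of the table.

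**5. What a specific outcome could show.** Counted without upper rebleeds, 2.5% against 1.0% at 1422 per group has about 86% power (two-sided 0.05), or about 83% with the continuity correction.

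**The case against.** **The sentence lists signs to watch for, not an event definition.** For upper bleeding, signs only trigger a work-up. This is fair as to wording, and it is why the point is stated for a literal reading. But no other text in the protocol turns the signs into a lower-bleeding event, and no confirming step is given.

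**Rectal blood may be required as well as another sign.** The text allows this, although an added list item is the more natural reading. Under it, not every upper rebleed would count, and rectal blood with a hemoglobin drop, transfusion or instability would be a usable, severity-restricted measure of lower bleeding. A reader might infer that the outcome fails to measure lower bleeding on either reading; that goes too far. What is lost is isolated rectal bleeding, and a brisk upper bleed could still qualify.

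**The trial would wrongly declare that rectal aspirin lowers both kinds of bleeding.** A reader might infer this from the reversed sign. The figures do not support it for a material harm: at 2.5% against 1.0% the result is z about −1.4 (p about 0.16), which is masking. A nominally significant false benefit is the expected result only when true harm is absent or small.

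**A statistical analysis plan may add source attribution.** It may, and Section C's endoscopy would supply much of the information. But the protocol itself fixes the criteria, and it puts hematemesis among the lower-bleeding signs.

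**The rates are not exactly those as written.** This stands. The literal reading would also admit unconfirmed signs such as tachycardia alone, so real counts could be higher than those shown.

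**Conclusion.** The point holds in conditional form. On the natural reading, every primary-outcome event also meets the lower-bleeding criteria; that overlap follows from the text and needs no assumed rate. The bias towards rectal aspirin additionally needs the hypothesised upper benefit. If 7% against 10% holds, the overlap can produce a false benefit when lower-bleeding rates are equal. It masks or reverses a true rectal excess of up to about 3.2 points. These sizes rest on assumed lower-bleeding rates, independence, and carrying over confirmed upper rebleeds only.

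The primary outcome and the sample size are not affected. Because this is one secondary outcome, and much of the information needed to separate the sources is already to be collected, it is a should-fix rather than a must-fix.

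**What to change.** In Section C, replace the shared list with an event definition for lower gastrointestinal bleeding:

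- The event is bright red blood per rectum, or one of the non-localising shared signs (melena, hemoglobin drop, transfusion, unstable vital signs), in an episode where the endoscopy that Section C already requires found no upper source.
- Isolated rectal blood is not one of the signs that trigger that endoscopy. State that such an episode counts as lower unless an upper source has been confirmed.
- Remove hematemesis from the lower-bleeding list.
- State that any one qualifying sign suffices.
- Assign each bleeding episode to one category, upper or lower.
- Report bright red blood per rectum separately by arm, so that the sign closest to the rectal site can be seen on its own.

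The cost is wording in the protocol and case-report form; no new procedure is needed. There will be fewer lower-bleeding events, and some episodes with a negative endoscopy will remain of uncertain origin. The separate report of rectal blood limits the effect of that uncertainty.

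### Aspirin levels are sampled by calendar day with no record of dose or draw time, so the planned comparison cannot separate time since dose from exposure

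*Protocol*

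**What the plan says.** Section B of the protocol lists among the secondary outcomes "lower gastrointestinal bleeding, and aspirin blood levels in the two groups". Section C sets the schedule: "Blood levels of aspirin will be measured at day 1, 15, 30". For discharged patients the later two samples are tied to a "clinic visit with a study physician at 15 and 30 days if not still in the hospital, when blood will be drawn".

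Dosing is double-dummy (section B): "The patients will receive both a po and rectal pill daily, one will be a placebo and the other pill will be active". The doses differ by arm (section C): patients "will be randomized to either 300mg aspirin administered rectally or 81 mg po aspirin".

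For analysis, section B gives the chi-squared test for the primary outcome and "a t-test to compare group differences". Aspirin level is the only listed outcome that is naturally a continuous measurement, so I read the t-test as applying to it.

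The levels bear on a premise in section A, that "rectal administration of aspirin can achieve the same blood levels as po administration". The only check on dosing is in section D: "A pill count will also be performed at the 30 day visit to ensure compliance with study medications".

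The protocol gives no hour for either tablet, does not say whether the two are taken together, sets no interval between dose and draw, and does not ask for any of these times to be recorded.

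**The concern.** A single blood level depends on how much drug was absorbed and on how long ago it was taken. With once-daily dosing and a draw at whatever hour the visit falls, the second can vary widely between patients.

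Randomisation balances visit hours and patients' habits between arms, but it does not balance the interval that matters. The clock runs from the oral tablet in one arm and from the rectal tablet in the other. If patients in both arms tend to take the oral tablet at one time of day and the rectal tablet at another, identical behaviour produces different active-dose-to-draw intervals. The double dummy conceals which tablet is active; it does not equalise these intervals.

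At stake is the interpretation of the secondary outcome that speaks most directly to whether the rectal arm received comparable systemic exposure. Section M describes the hoped-for benefit as less rebleeding with the mortality benefit kept, so a level comparison that cannot be read weakens the explanation of any rebleeding difference.

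This is not a detail that can wait for an analysis plan. Dose and draw times are conduct data, and times that were never recorded cannot be recovered later.

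**Working it through.** **The plan's own figures.** The protocol states no figure for the level comparison. Its one sample-size figure, for the primary outcome, reproduces and is not in question. With 7% versus 10%, two-sided 0.05, 80% power and 1:1 allocation, the uncorrected formula gives 1356 per group, and the continuity-corrected formula gives 1422, as stated.

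**Inputs from the protocol.** One oral and one rectal tablet daily, one of them active (section B); 300 mg rectal and 81 mg oral (section C); sampling on days 1, 15 and 30 (section C); a t-test (section B).

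**Inputs assumed.** The protocol gives no half-life and no gap between the tablets. I take half-lives of 2, 3 and 6 h and a 4 h gap as illustrations.

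**Step 1: apparent ratio from timing alone.** With equal true exposure, first-order decline and absorption complete, the ratio of levels is 2^(gap/half-life):

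- half-life 2 h: 2^(4/2) = 4.0
- half-life 3 h: 2^(4/3) = 2.5
- half-life 6 h: 2^(4/6) = 1.6

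A shorter half-life raises it (1 h: 2^4 = 16). With no gap the ratio is 1 at any half-life.

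**Step 2: comparison with the dose ratio.** The nominal dose ratio is 300/81 = 3.70, and log2(3.70) = 1.89 half-lives. A gap of that length would cancel the whole nominal dose ratio in one direction, or square it in the other:

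- half-life 2 h: 1.89 × 2 = 3.8 h
- half-life 3 h: 1.89 × 3 = 5.7 h
- half-life 6 h: 1.89 × 6 = 11.3 h

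**Step 3: what the t-test does.** This was simulated with equal true exposure in both arms, steady once-daily dosing, draws spread evenly from 1 to 9 h after the oral tablet, a log-scale SD of 0.3 between patients, half-lives of 1, 3 and 6 h, and 400 runs per setting. All of these are assumptions.

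- Tablets together, equal absorption rate: the test rejected in about 4% to 6% of runs, close to the nominal level. Untimed draws were noise, not bias.
- Active rectal dose 4 h further from the draw: it rejected in every run, with 100 or 1422 per arm. The rectal-to-oral ratio of means was 0.40 at a half-life of 3 h and 0.63 at 6 h.
- Tablets together, slower rectal absorption: at 1422 per arm it rejected in 10% to nearly 100% of runs, with ratios of means from 1.01 to 1.25. One untimed sample also mixes the absorption profile with exposure.

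**The case against.** The strongest reply is that the bias is conditional. Section B says only that both tablets are received daily. If they are taken together, randomisation and the double dummy give time since dose the same distribution in both arms. This stands. A reader might infer that the comparison does reflect time since dose instead of exposure; the protocol does not show that. It shows only that the two cannot be told apart.

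The magnitudes are also assumed. A reader might choose a 10 h gap and obtain 32-fold at a half-life of 2 h (2^(10/2)), or say that the artefact matches or exceeds the dose ratio. The protocol supports neither. At a 4 h gap, two of the three ratios above fall below 3.7, so the same order is as far as one can go. The formula also assumes absorption is complete, although absorption by route is part of the question.

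Three further limits stand:

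- The arms differ in dose as well as route, so even perfectly timed levels compare 300 mg rectal with 81 mg oral, not route alone.
- Eligible patients were already on aspirin and no pre-dose sample is scheduled on day 1. A reader might see bias there, but earlier use precedes randomisation and is balanced on average. It can blur a day 1 difference; it does not favour an arm. Dosing at home is also not an issue for patients still in hospital.
- A reader might conclude that less rebleeding could then never be distinguished from less absorption. That goes too far: ischaemic events and mortality also bear on whether aspirin's effect is kept, and the pill count checks intake. The pill count gives number, though, not time, so it does not repair the level comparison.

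**Conclusion.** The point holds in a limited form. Sampling is tied to calendar days only, no dose or draw time is asked for, and the active tablet differs by arm. The planned t-test on aspirin levels therefore cannot separate time since dose from exposure. Whether this produces bias or mainly noise depends on when patients take the two tablets, which the protocol leaves open.

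If there is a habitual gap, the effect could be material: about 1.6- to 4-fold for 4 h at half-lives of 6 to 2 h, against a nominal dose ratio of 3.7. The gap, the half-lives and completed absorption are assumptions. The finding touches one secondary outcome. The primary outcome and the 1422 per group are unaffected. It is a cheap improvement worth making before enrolment.

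**What to change.** Add to section C that at each sample on days 1, 15 and 30 the clock times of the last oral tablet, the last rectal tablet and the blood draw are recorded, and that draws are scheduled, where feasible, within one common window after the last study tablets, the same in both arms. The window's limits need to be stated. Recording both tablet times keeps sites blinded, because the time since the active dose is derived only once allocation is known at analysis.

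In section B, replace the unadjusted t-test for this outcome with a model that includes time since the active dose, for example a regression of log level on arm and that time. Keep all samples, including those outside the window; dropping them would be an exclusion after randomisation. Describe the result as a comparison of the two regimens (dose plus route), not of route alone.

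The cost is three time fields per sample and some scheduling effort at visits already planned. With 2 × 1422 = 2844 patients and two visits each, there are up to 5688 such visits, so the window should be a scheduling aim and not a compulsory wait. Nothing here needs to prescribe when tablets are taken. One timed sample will still not measure full exposure, and adjustment works poorly if the intervals in the two arms hardly overlap, which is why the common window is worth attempting.
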